The immunogenicity analysis will be performed overall, by sex, age category (age at Dose $1: \ge 65$ YOA, ≥ 70 YOA, ≥ 80 YOA, 60-69 YOA and 70-79 YOA, and region (North America, Europe, Asia).

5.4.3. Additional considerations

5.4.3.1. Mixed effects model

For the GMTs/GMCs calculation based on the mixed effects model mentioned in Section 5.3.1.1, repeated measures analysis of covariance (ANCOVA) model will be fitted including age category (60-69 YOA , 70-79 YOA and \geq 80 YOA,), study group (RSV_annual, RSV_flexible revaccination and RSV_1dose), sex (male and female), visit (Day 31, Months 6, 12, 13, 18, 24, 25, 30, 36), as fixed effects, pre-vaccination log10-transformed titers/concentrations as a covariate and the response variable is the post-vaccination log10-transformed titers/concentrations. The PROC MIXED procedure in SAS® will be used to carry out the ANCOVA.

The following SAS codes will be used:

For the analysis by study group, study group and visit will be included as the fixed effects in the model

```
Analysis by group
PROC MIXED DATA=SERO method=reml empirical;
CLASS subjid group visit ;
MODEL post-vac=pre-vacc group visit visit*group/ noint s cl;
RANDOM intercept/ subject=usubjid g v vcorr type = un;
REPEATED visit/type=unsubject=subjid;
LSMEANS visit*group/ E cl;
ODS OUTPUT LSMEANS=LS;
RUN;
```

For the analysis by age category, age category and visit will be included as the fixed effects in the model. However, this is only applicable at timepoints where the 3 study groups will be pooled. Otherwise for the timepoints where pooling of the 3 groups is not possible, the fixed effects will include study group, age category and visit.

Analysis by age-category

```
PROC MIXED DATA=SERO method=reml empirical ;
CLASS subjid visit agecat ;
MODEL post-vac=pre-vacc agecat visit visit* agecat /noint s cl;
RANDOM intercept/ subject=usubjid g v vcorr type = un;
REPEATED visit/type=un subject=subjid;
LSMEANS visit*agecat/ E cl;
ODS OUTPUT LSMEANS=LS;
RUN;
```

For the analysis by sex, sex and visit will be included as the fixed effects in the model. However, this is only applicable at timepoints where the 3 study groups will be pooled. Otherwise for the timepoints where pooling of the 3 groups is not possible, the fixed effects will include study group, sex and visit.

Analysis by sex

```
PROC MIXED DATA=SERO method=reml empirical;
CLASS subjid visit agecat ;
MODEL post-vac=pre-vacc sex visit visit* sex / noint s cl;
RANDOM intercept/ subject=usubjid g v vcorr type = un;
REPEATED visit/type=un subject=subjid;
LSMEANS visit*sex/ E cl;
ODS OUTPUT LSMEANS=LS;
RUN;
```

For the analysis by region, region and visit will be included as the fixed effects in the model. However this is only applicable at timepoints where the 3 study groups will be pooled. Otherwise for the timepoints where pooling of the 3 groups is not possible, the fixed effects will include study group, region and visit.

Analysis by region

```
PROC MIXED DATA=SERO method=reml empirical;
CLASS subjid visitregion ;
MODEL post-vac=pre-vacc region visit visit* region / noint scl;
RANDOM intercept/ subject=usubjid g v vcorr type = un;
REPEATED visit/type=un subject=subjid;
LSMEANS visit*region/ E cl;
ODS OUTPUT LSMEANS=LS;
RUN;
```

The GMTs/GMCs, lower and upper confidence limits are obtained from the following data step:

```
DATA LS;
   SET LS;
   gm=10**estimate;
   ll=10**lower;
   ul=10**upper;
RUN;
```

The above SAS codes may be adapted in case of convergence issues.

5.4.3.2. Cell-mediated immune response

Within groups evaluation

- The frequency of RSVPreF3 specific-CD4+ T cells will be displayed graphically using boxplots (min, Q1, median, Q3, max), by group and timepoint.
- The RSVPreF3-specific CD4+/ CD8+ T cell frequencies will be obtained by subtracting the background value to the antigen-induced value, and by setting to 1 all values less than or equal to zero for geomean calculation and graphical representation. Frequencies will be expressed as the number of cells per million of CD4+ T cells.
- More specifically, the frequencies of RSVPreF3-specific CD4+/ CD8+ T cells expressing at least 2 activation markers including at least one cytokine [*Freq*²⁺] will be computed as follows:

$$Freq_{Background}^{2+} = \frac{n_{background}^{2+}}{N_{Background}^{CD4}} \quad \text{and} \quad Freq_{Induction}^{2+} = \frac{n_{Induction}^{2+}}{N_{Induction}^{CD4}},$$

And

$$Freq_{Specific}^{2+} = Freq_{Induction}^{2+} - Freq_{Background}^{2+}$$

where

 $n_{Background}^{2+}$ = number of CD4+ T cells expressing at least 2 activation markers including at least one cytokine after stimulation with medium only (background),

 $n_{Induction}^{2+}$ = number of CD4+ T cells expressing at least 2 activation markers including at least one cytokine after stimulation with a pool of peptides covering RSVPreF3 (induction),

 $N_{Back/Ind}^{CD4}$ = Total number of CD4 T cells involved in the assay (background or induction).

For the computation of the fold increase (post- over pre-vaccination) of the frequency of RSVPreF3-specific CD4+ T-cells identified as expressing **at least 2 activation marker(s) including at least one cytokine*** among CD40L, 4-1BB, IL-2, TNF- α , IFN- γ , IL-13, IL-17.the results below the LLOQ of the assay will be replaced by the value of the LLOQ.

* cytokines are IL-2, TNF-α, IFN-γ, IL-13, and IL-17

5.4.3.3. Assessment of long-term persistence of the immune response at Months 18, 24 and 36 after dose 1

The exploratory analysis for modelling the long-term persistence of immune response (humoral and cellular) post dose 1 vaccination will constitute of the following;

- A piece-wise linear mixed model, power law model and modified power law model [David et al, 2009] for repeated measurements (all data available from Day 31, Month 6, 12, 18, 24, 30, 36 post-Dose 1 vaccination, will be used to model over time
 - the frequency of RSVPreF3-specific CD4+ T cells expressing at least 2 activation markers including at least one cytokine among CD40L, 4-1BB, IL-2, TNF-α, IFN-γ, IL-13, IL-17.
 - the neutralizing antibody titers against RSV-A, RSV-B and RSVPreF3-specific IgG antibody concentrations.

The *piece-wise linear mixed model* is expressed as follows

The piece-wise model fits the data on non-overlapping time intervals. This corresponds to the observed decay of humoral and cellular antibodies. Each piece of the model uses a linear function. Break points will be selected on the basis of Akaike's Information Criterion (AIC) [Pan, 2001].

$$(ft) = \beta_0 + \beta_1 t \quad \text{if } x \le t < xx \text{ months}$$
$$(ft) = \beta_0 + \beta_1 t + \beta_2 (t - xx) \quad \text{if } xx \le t < xxx \text{ months}.$$
$$(ft) = \beta_0 + \beta_1 t + \beta_2 (t - xx) + \beta_3 (t - xxx) \quad \text{if } t \ge xxx \text{ months}$$

where f(t) is the log-10 transformed antibody titer/concentration/ RSVPreF3-specific CD4+ T cells at time t post-vaccination, β_0 is the intercept and $\beta_1(i = 1,2,3...)$ are the

Statistical Analysis Plan Amendment 3

parameters corresponding to the time intervals, respectively. All the model effects will be fitted using the SAS PROC MIXED standard code for linear regression methodology for repeated data.

```
ODS OUTPUT FitStatistics= stat;
ODS OUTPUT ConvergenceStatus= conv;
PROC MIXED DATA=kin&i.&j. EMPIRICAL COVTEST NOCLPRINT IC;
CLASS pid;
MODEL log_val = int_m int_m_pw_m&i.*m&i. int_m_pw_m&j.*m&j./s cl
covb outp=pred outpm=predm;
RANDOM intercept/SUBJECT=pid;
MAKE "solutionF" out=est;
RUN;
```

The *power-law model* is expressed as follows:

 $f(t) = k - a \log(c + t)$

where f(t) is the log-10 transformed antibody titer/concentration/ RSVPreF3-specific CD4+ T cells at time t post-vaccination, k is the peak log level, a is the decay rate, and c is an arbitrary small constant (set to zero in this case). The estimated maximum likelihood (ML) values for the model parameters will be obtained using the PROC NLMIXED SAS procedure.

```
PROC NLMIXED DATA=kineticm;
PARMS se=&se a0 =&a k0 =&k sk=&sk sa=&sa ska=&ska;
q = (1/&time)**a;
lg=&log(q);
mean = k + lg;
MODEL log_val ~ NORMAL(mean,se*se);
RANDOM k a ~ NORMAL([k0,a0], [sk*sk, ska, sa*sa]) SUBJECT=pid out=indiv;
RUN;
```

The *modified power-law model* is expressed as follows:

It is an extension of the power law model, and it is expressed as follows.

 $f(t) = k + \log[(1 - \pi)(c + t)^a + \pi]$

The quantity π (between 0 and 1) represents the proportion of antibodies that are produced in the long term. When the value of π is positive, this implies long-term antibody persistence, as noted by [Fraser et al, 2007]. If $\pi = 0$, then the modified power-law model reduces to the standard power-law model. The estimated maximum likelihood (ML) values for the model parameters will be obtained using the PROC NLMIXED SAS procedure.

```
PROC NLMIXED DATA=kineticm ;
PARMS pi=&pi se=&se a0 =&a k0 =&k sk=&sk sa=&sa ska=&ska;
q = (1-pi)*(1/&time)**a;
lg=&log(q+pi);
mean = k + lg;
MODEL log_val ~ NORMAL(mean,se*se);
RANDOM k a ~ NORMAL([k0,a0], [sk*sk, ska, sa*sa]) SUBJECT=pid out =indiv
RUN;
```

- The three models based on data up to Month 36 will be presented graphically. Models based on data up to Month 18 vs. Month 24, Month 24 vs. Month 30 and Month 30 vs. Month 36 will be presented side by side.
- The above models and SAS codes may be adapted in case of convergence issues.

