9.2. Sample size determination (Amended: 01 April 2022)

This study is planned to enroll ~1650 participants randomized according to 3:1:1 ratio to 1 of the 3 study groups: RSV_annual, RSV_flexible revaccination, and RSV_1dose respectively.

The proposed sample size is based on the following considerations:

• Ensure a sufficient number of participants to evaluate with adequate precision the immunogenicity after a single dose regimen up to 12 months post-vaccination (based on the 3 pooled RSV_annual, RSV_flexible revaccination and RSV_ldose groups) but also the immunogenicity after revaccination (based on RSV_annual and RSV_flexible revaccination groups).

- Ensure adequate description of the antibody kinetics after a single dose keeping the flexibility to give a revaccination to a part of the participants.
- Ensure an adequate sample size for evaluation of reactogenicity and safety profile following revaccination.

Approximately 345 participants will be enrolled in the humoral subset in the RSV_annual group and approximately 330 participants per group in the RSV_flexible revaccination and RSV_1dose groups. Approximately 345, 115 and 115 participants will be enrolled in the CMI subset in the RSV_annual, RSV_flexible revaccination, and RSV_1dose groups, respectively. A total of 990 and 330 participants will be enrolled in the RSV_annual and RSV_flexible revaccination groups, respectively, for evaluation of reactogenicity and safety profile following revaccination. A 20% rate of non-evaluable participants every year will be considered.

Withdrawals will not be replaced.

9.2.1. Evaluation of humoral immune response up to Month 12 (primary objective and first secondary objective)

At Month 12, the effect of a 1-dose primary schedule will be evaluated in terms of RSV-A/B neutralizing antibody titers and RSVPreF3-specific IgG concentrations. Approximately 804 participants in the (RSV_annual, RSV_flexible revaccination, and RSV_1dose) pooled group receiving a single dose of RSVPreF3 OA investigational vaccine will be evaluable for the humoral immune response at Month 12.

Table 17 shows the precision that can be obtained based on different values of standard deviations in terms of RSV-A/B neutralizing antibody titers, and RSVPreF3-specific IgG antibody concentrations.

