9.4.5. Tertiary/exploratory endpoints (Amended: 01 April 2022)

Please refer to the SAP for statistical analyses concerning tertiary endpoints and modeling of long-term persistence of post-primary vaccination antibodies (using mixed *effects* models for repeated measurements).

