Study Groups	Number of participants	Age	Primary vaccination	Revaccination Year 1 (Month 12)	Revaccination Year 2 (Month 24)	Open
RSV_annual*	~990	≥60 years	RSVPreF3 OA investigational vaccine	RSVPreF3 OA investigational vaccine	RSVPreF3 OA investigational vaccine	х
RSV_flexible revaccination	~330	≥60 years	RSVPreF3 OA investigational vaccine	(none)	RSVPreF3 OA investigational vaccine	х
RSV_1dose	~330	≥60 years	RSVPreF3 OA investigational vaccine	(none)	(none)	х

* RSV_annual group will be split in 3 technical groups in SBIR in order to have a randomization ratio of 1:1:1:1:1: for treatment allocation and avoid predictability.

• **Groups and sub-groups definition for analysis:** Refer to the tables below for a description of the groups and subgroups labels that will be used in the Tables Figures and Listings (TFLs).

The analyses pertaining to timepoints up to Month 12 will be performed for each group and for the 3 groups pooled. From Month 13 up to study end, the analyses will be performed by group.

The following group names will be used in the TFLs:

Table 2 Group names and definition for footnote in the TFLs

Group order in tables	Group label in tables	Group definition for footnote	
1	RSV_annual	Participants receiving the first dose (Dose 1) of RSVPreF3 OA investigational vaccine at Day 1, followed by a revaccination dose at 12 months post-Dose 1 and at 24 months post-Dose 1	
2	RSV_flexible revaccination	Participants receiving the first dose (Dose 1) of RSVPreF3 OA investigational vaccine at Day 1 and a revaccination dose at 24 months post-Dose 1	
3	RSV_1dose	Participants receiving a single dose (Dose 1) of RSVPreF3 OA investigational vaccine at Day 1	

Pooled Group label in tables	Groups to be pooled	Pooled definition for footnote	Comment
Total	RSV_annual, RSV_flexible revaccination and RSV_1dose	Participants receiving one dose of RSVPreF3 OA investigational vaccine at Day 1 in all the three groups	Applicable on data reported up to Month 12
Flexible+1dose	RSV_flexible revaccination, and RSV_1dose	Participants receiving one dose of RSVPreF3 OA investigational vaccine at Day 1 in the RSV_flexible revaccination, and RSV_1dose groups	Applicable on data reported at Month 13, Month 18 and Month 24

Table 3Pooled group names and definition for footnote in the TFLs

Table 4Sub-group names and definitions for footnote in the TFLs

Sub-analysis	Subgroup order in tables	Subgroup label in tables	Subgroup definition for footnote

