5. STATISTICAL ANALYSES

Standard data derivation rules and stat methods are described in Section 10.1 while the study specific data derivation rules and stat methods are described in Section 9.

For the sake of analysis, data up to Month 12 will be analyzed by group (RSV_annual, RSV_flexible revaccination and RSV_1dose), and also the 3 groups will be pooled. For Month 13, Month 18 and Month 24, the analyses will be tabulated for RSV_annual group versus the pooled RSV_flexible revaccination and RSV_1dose groups. From Month 25 up to study end, the analyses will be performed by group

If more than 5% of participants in the RSV_annual and RSV_flexible revaccination groups receive different number of doses, an analysis by subgroup according to the number of dose(s) administered might be performed. The goal of this analysis is to describe the characteristics of participants in the RSV_annual and RSV_flexible revaccination groups who ultimately receive different numbers of revaccination doses in order to rule out the possibility of systematic differences between these subgroups.

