5.4. Secondary endpoint(s)

5.4.1. Humoral immune response

The same analyses as described above for the primary endpoint will be performed for RSVPreF3-specific IgG ELISA up to Month 12 and for each timepoint with blood sample collection for humoral immune response **from study Month 13 up to study end** and for each assay (RSVpreF3-specific IgG **ELISA and RSV-A/-B neutralization assays**). For Month 13, Month 18, and Month 24, the analyses will be tabulated for RSV_annual group versus the pooled RSV_flexible revaccination and RSV_1dose groups. From Month 25 up to study end, the analyses will be performed by group.

Only the analyses requiring further clarification of the exact timepoints analyzed are summarized below:

Within groups evaluation:

- The MGI i.e. geometric mean of ratios of antibody titer/concentrations will be tabulated with 95% CI:
 - For each post-primary vaccination time point (at Months 18, 24, 30 and 36 when applicable) over pre-primary vaccination (Day 1),
 - For each post-revaccination time point over corresponding pre-revaccination (Months 12 and 24) in the RSV_annual group,
 - For each post-revaccination timepoint over corresponding pre-revaccination (Month 24) in the RSV_flexible revaccination group,
 - For 1 month post-revaccination at Month 12 (Month 13) over 1 month post-Dose 1 vaccination (Day 31) in RSV_annual group.
 - For 1 month post-revaccination at Month 24 (Month 25) over 1 month post-revaccination at Month 12 (Month 13) in RSV_annual group
 - For 1 month post-revaccination at Month 24 (Month 25) over 1 month post-Dose 1 vaccination (Day 31) in RSV_flexible revaccination group.

In addition, the following evaluation will be performed:

• The kinetics of GMTs/GMCs will be plotted as a function of time for participants with results available at all post vaccination timepoints.

The immunogenicity analysis will be performed overall, by sex, age category (age at Dose $1: \ge 65$ YOA, ≥ 70 YOA, ≥ 80 YOA, 60-69 YOA and 70-79 YOA), and region (North America, Europe, Asia).

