5.4.3.4. Sensitivity analyses

- In case the COVID-19 pandemic is still ongoing during the study conduct, the following sensitivity analyses might be considered.
 - During the assessment of long-term persistence of the immune response, the models described in Section 5.4.3.3 might be fitted taking into account participants who received the first dose of study vaccine and with full follow-up (attending all study visits).
 - Similarly, a mixed model might be fitted for the evaluation of GMT/GMC based on participants with full follow-up (attending all study visits).

The goal of this sensitivity analysis is to determine the extent to which results might be impacted by considering the different scenarios.

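### SAP 5.4.3.3 sets no cut at revaccination for the exploratory dose-1 persistence models, so as written, samples taken after a booster enter a dose-1 decay curve

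*SAP*

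**What the plan says.** SAP Amendment 3, 5.4.3.3, is an exploratory analysis of persistence after dose 1. It fits a piece-wise linear mixed model, a power law and a modified power law to antibody titers/concentrations and CD4+ T-cell frequencies. The data rule is that "all data available from Day 31, Month 6, 12, 18, 24, 30, 36 post-Dose 1 vaccination, will be used to model over time". No group is named. The printed code has no group term, no filter and no booster indicator, and it reads datasets whose construction is not described. The section treats a positive plateau in the modified power law as long-term persistence.

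The dosing is in SAP 3.1 (Tables 1 and 2): RSV_annual receives doses at Day 1, Month 12 and Month 24; RSV_flexible at Day 1 and Month 24; RSV_1dose at Day 1 only. SAP 5.4.1 treats Month 12 (RSV_annual) and Month 24 (both revaccinated groups) as pre-revaccination samples.

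The general grouping rules are elsewhere. In Table 3 the three-group pool is "Applicable on data reported up to Month 12", and RSV_flexible and RSV_1dose are pooled at Months 13, 18 and 24. SAP section 5 adds: "From Month 25 up to study end, the analyses will be performed by group".

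**The concern.** A decay curve for dose 1 should contain only samples that reflect dose 1. Under the stated rule, RSV_annual contributes Months 18, 24, 30 and 36 after at least one booster, and RSV_flexible contributes Months 30 and 36 after its booster. The late visits determine the long-term slope and the plateau, and they hold the largest share of boosted samples.

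Persistence up to three years after a single dose is a stated study purpose (Protocol 2.1). If boosted levels differ from what the same people would have had unboosted, the decay parameter and the plateau no longer describe one dose. Two analysts following 5.4.3.3 could also produce different curves, one filtering at revaccination and one not.

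**Working it through.** **1. Reproduce the plan's counts.** Subset sizes (SAP 3.1) for RSV_annual / RSV_flexible / RSV_1dose are 345 / 330 / 330 (humoral) and 345 / 115 / 115 (CMI). Totals: 345 + 330 + 330 = 1005 and 345 + 115 + 115 = 575. Revaccinated groups only: 345 + 330 = 675 and 345 + 115 = 460. All four match Protocol Table 13. The 20% yearly loss (Protocol 9.2) gives 1005 × 0.8 = 804, as in Table 17.

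**2. Count samples after a booster at the seven listed visits, before attrition.**

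| Visit | Humoral | CMI |
|---|---|---|
| Day 31, Months 6, 12 | 0 of 1005 each | 0 of 575 each |
| Months 18, 24 | 345/1005 = 34% each | 345/575 = 60% each |
| Months 30, 36 | 675/1005 = 67% each | 460/575 = 80% each |
| All seven visits | (345×4 + 330×2)/(7×1005) = 2040/7035 = 29% | (345×4 + 115×2)/(7×575) = 1610/4025 = 40% |
| After Month 12 | 2040/4020 = 51% | 1610/2300 = 70% |

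If the 20% yearly loss is spread evenly over time and groups (assumption), the overall shares are about 23% (1200/5142) and 33% (967/2942).

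**3. Effect on the fit (illustration).** The documents give no boosted-to-unboosted ratio, so every input here is assumed: true decay a = 0.3, true plateau 0, all groups in one curve, least squares on the seven humoral visit means.

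- Power law (c = 0): f(t) = k − a·log10(t).
- Modified law, with the sign used in the printed code: f(t) = k + log10[(1 − π)·t^(−a) + π].

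Scenario A: boosted samples are r times the unboosted level, so the visit mean is −0.3·log10(t) + share × log10(r). For r = 1.5, log10(r) = 0.176; the shift is 0.343 × 0.176 = 0.060 at Months 18 and 24, and 0.672 × 0.176 = 0.118 at Months 30 and 36.

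Scenario B: one month after each booster the log level has regained a fraction R of what was lost, and the same decay then restarts.

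| Scenario | Boosted/unboosted ratio | Fitted decay (power law) | Fitted plateau (modified law) |
|---|---|---|---|
| A, r = 1 | 1 | 0.30 | 0 |
| A, r = 1.25 | 1.25 | 0.26 | 0.27 |
| A, r = 1.5 | 1.5 | 0.22 | 0.40 |
| B, R = 50% | 0.79–1.01 | 0.32 | 0 |
| B, R = 70% | 0.98–1.22 | 0.28 | 0.13 |
| B, R = 100% | 1.23–1.62 | 0.23 | 0.38 |

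Decay therefore runs from about 0.22 to 0.32 and the plateau from 0 to about 0.40. With the CMI shares the ranges are wider: 0.20 to 0.33, and 0 to 0.46. With a cut at first revaccination, the power law recovers 0.30 in every scenario.

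**4. Does another rule supply the cut?**

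- Months 13 and 25 are not in the 5.4.3.3 list, whereas the mixed model in 5.4.3.1 uses "visit (Day 31, Months 6, 12, 13, 18, 24, 25, 30, 36), as fixed effects". That removes the one-month booster peaks but leaves Months 18 to 36.
- The term post-Dose 1 is also the visit clock for all groups in the endpoint table (SAP section 2).
- The pooling rules in Table 3 and SAP section 5 set groupings and drop no samples.
- Elimination code 1070 (Table 6) covers unplanned revaccination and several administration faults, not scheduled boosters.
- The full-follow-up sensitivity set in 5.4.3.4 keeps boosted participants.

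**The case against.** The strongest reply is that exclusion is already meant. The heading and purpose of 5.4.3.3 refer to dose 1, the text describes decay from a peak, and Protocol 9.4.5 describes "modeling of long-term persistence of post-primary vaccination antibodies". Protocol 9.2 lists as an aim: "Ensure adequate description of the antibody kinetics after a single dose". SAP 5.4.1 separates post-primary from post-revaccination timepoints, and the unnamed input datasets could be filtered. The February 2021 SAP used only RSV_flexible and RSV_1dose in these models from Month 13. That text is superseded and the difference is not itself an error, but it fits a drafting omission. All this stands as evidence of intent. None of it is a rule in the current SAP. Restoring the 2021 limit would not be enough either, because RSV_flexible is now revaccinated at Month 24.

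A second reply is that the booster effect may be small. Protocol 4.3 reports no added value of a second dose given at 2 months. Protocol 4.2 says a later revaccination induced responses but gives no comparison with unboosted participants. At a ratio of 1 there is no bias.

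Two stronger readings are tempting. A reader might infer that persistence will be overstated. The documents do not support a direction: at 50% restoration the fitted decay is too steep and the plateau is 0. A reader might also infer that separate RSV_annual and RSV_flexible curves will be biased by a calculable amount. Section 5.4.3.3 never says curves are fitted by group, so figures resting on that assumption should not lead.

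**Conclusion.** The concern holds as a defect in the stated data rule. Followed as written, 5.4.3.3 puts 29% of planned humoral and 40% of planned CMI samples into a dose-1 model after a scheduled booster, with 67% and 80% at Months 30 and 36. Those counts rest only on the planned subset sizes and dosing schedule. The effect on decay and plateau rests wholly on assumed booster responses and a pooled fit; its size and sign cannot be read from the documents.

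The reach is limited. The models are exploratory and all analyses are descriptive. The Month 12 primary endpoint is unaffected, as are the RSV_1dose GMT/GMC tables, which report single-dose persistence directly. A reader should not conclude that the sponsor intends to include boosted samples, or that the trial's single-dose results are compromised. The text should be corrected before the Month 36 models are run.

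**What to change.** State in 5.4.3.3 that each participant contributes only samples taken before the first revaccination actually received. On the planned schedule this means:

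- all three groups up to the pre-dose Month 12 sample;
- RSV_flexible and RSV_1dose up to the pre-dose Month 24 sample;
- RSV_1dose only at Months 30 and 36.

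State also whether the curves are pooled or by group, consistently with Table 3 and SAP section 5. Any curve after a booster should be a separate model on time since the last dose.

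The cost is one sentence and a data filter. Planned samples fall to 7035 − 2040 = 4995 (humoral) and 4025 − 1610 = 2415 (CMI). At Months 30 and 36 only 330 of 1005 humoral and 115 of 575 CMI participants contribute before attrition. With 20% yearly loss, Month 36 has about 330 × 0.8³ = 169 and 115 × 0.8³ = 59.

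The loss for the whole curve is smaller. Under five assumed sets of standard deviations for a power law with random k and a, the standard error of the decay is 8–15% larger (humoral) and 13–25% larger (CMI) than with unfiltered data. It is 34–38% and 44–49% smaller than with RSV_1dose alone, which would also remove the problem but at that cost in precision.
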